### 8.3. Patient Rescreening

Patients may repeat the screening procedures once to qualify for the study if they have:

- Taken systemic corticosteroids within 30 days prior to Study Day 1 (rescreening may be performed 30 days or more after discontinuation of corticosteroids)
- Used antioxidant supplements, including but not limited to idebenone, coenzyme Q10, nicotinamide, and vitamin E above the recommended daily allowance, within 14 days prior to Study Day 1 (rescreening may be performed 14 days or more after discontinuation of supplement)
- Participated in any other interventional clinical study within 30 days prior to Study Day 1 (rescreening may be performed 30 days or more after completion of the clinical study)
- An abnormal laboratory test value that may normalize, in the opinion of the investigator (rescreening may be performed once test value is within normal range)
- Modified their exercise regimen within 30 days prior to Study Day 1 (rescreening may be performed 30 days or more after modification of exercise regimen)
- Taken any of the following drugs within 7 days prior to Study Day 1 (rescreening may be performed 7 days or more after discontinuation of the drug):
  - Sensitive substrates for cytochrome P450 2C8 or 3A4 (e.g., repaglinide, midazolam, sildenafil)
  - Moderate or strong inhibitors or inducers of cytochrome P450 2C8 or 3A4 (e.g., carbamazepine, phenytoin, ciprofloxacin, grapefruit juice)
  - Substrates for p-glycoprotein transporter (e.g., ambrisentan, digoxin)
- Failed screening because of operational challenges (rescreening may be performed no fewer than 2 weeks from the date of screen failure)

## 8.4. Patient Discontinuation and Termination

Patients have the right to withdraw from the study at any time for any reason, without prejudice to their medical care. Furthermore, the investigator may discontinue a patient from study drug or terminate the patient from the study. The reason for a patient's withdrawal or discontinuation from the study will be recorded in the electronic case report form (eCRF).

### 8.4.1. Patient Discontinuation Criteria

Discontinuation refers to a patient stopping administration of study drug. Reasons for study drug discontinuation may include the following:

- Occurrence of an AE or change in medical status that leads the investigator to be concerned about the patient's welfare
- Protocol violations
- Administrative reasons (e.g., inability to continue)
- Sponsor termination of the study
- Voluntary withdrawal
- Pregnancy during the study
- Investigator unblinding

Patients who are discontinued from study drug should still complete all study visits and undergo all scheduled study assessments, if possible.

#### 8.4.2. Patient Termination Criteria

Termination refers to a patient stopping study drug and all study assessments and visits. Reasons for study termination include the following:

- Administrative reasons (e.g., inability to continue, lost to follow-up)
- Death
- Withdrawal of consent

Patients who terminate the study for any reason may not re-initiate study drug or study assessments at any time.

# 9. TREATMENT OF PATIENTS

### 9.1. Description of Study Drug

Depending on cohort dose level (or doses selected for Part 2), patients will ingest either 3 or 4 capsules of study drug (1 from each bottle included in study treatment kit) daily throughout the study; study drug is described in Section 10.1. Treatment kits containing up to 30 mg of RTA 408 will include three bottles, each containing 30 count of either active or placebo capsules. Treatment kits containing greater than 30 mg of RTA 408 will be comprised of four bottles, each containing 30 count of either active or placebo capsules. To maintain the study blind, treatment kits used in Part 2 will all include the same number of bottles. The Sponsor will provide sufficient quantities of study drug to allow for completion of the study.

### 9.2. Prior and Concomitant Medications

#### 9.2.1. Excluded Medications

Patients who have taken any of the following drugs within 30 days prior to Study Day 1 will be excluded from the study:

- Any other investigational drug
- Systemic corticosteroids

Patients who have taken any of the following drugs within 14 days prior to Study Day 1 will be excluded from the study:

• Antioxidant supplements, including but not limited to idebenone, coenzyme Q10, nicotinamide, and dosages exceeding the recommended daily allowance of vitamin E

Patients who have taken any of the following drugs within 7 days prior to Study Day 1 will be excluded from the study:

- Herbal preparations, minerals, or over-the-counter medication, except as identified in Section 9.2.2
- Sensitive substrates for cytochrome P450 2C8 or 3A4 (e.g., repaglinide, midazolam, sildenafil)
- Moderate or strong inhibitors or inducers of cytochrome P450 3A4 (e.g., carbamazepine, phenytoin, ciprofloxacin, grapefruit juice)
- Substrates for p-glycoprotein transporter (e.g., ambrisentan, digoxin)

The following medications and medication classes are not permitted during this study, except as noted in Section 9.2.2:

- Any other investigational drug
- Systemic corticosteroids
- Antioxidant supplements, including but not limited to idebenone, coenzyme Q10, nicotinamide, and dosages exceeding the recommended daily allowance of vitamin E

- Herbal preparations, vitamins, minerals, or over-the-counter medication, except as identified in Section 9.2.2
- Sensitive substrates for cytochrome P450 2C8 or 3A4 (e.g., repaglinide, midazolam, sildenafil)
- Moderate or strong inhibitors or inducers of cytochrome P450 3A4 (e.g., carbamazepine, phenytoin, ciprofloxacin, grapefruit juice)
- Substrates for p-glycoprotein transporter (e.g., ambrisentan, digoxin)
- Any interventional therapy intended to treat the mitochondrial myopathy disease condition, with the exception of a constant exercise regimen

### 9.2.2. Permitted Medications

The following concomitant medications are permitted, as authorized by the treating physician:

- Antibiotics, except as noted above (Section 9.2.1)
- Daily multivitamin
- Pain medication, except as noted above (Section 9.2.1)
- Other medications intended to manage concurrent diseases, except as noted above (Section 9.2.1)
- Oral, implantable, or injectable contraceptives

Patients taking medication chronically should be maintained on those same doses and dose schedules throughout the study period, as medically feasible. Patients taking medications with intermittent or as-needed schedules should try to avoid taking the concomitant medication on days when PK samples will be collected (i.e., Visits 4, 6, 8, and 11), as medically feasible.

# 9.3. Compliance With Study Drug

The investigator or designee will only dispense study drug to patients randomized to study treatment in accordance with the protocol. The study drug must not be used for reasons other than that described in the protocol.

All patients will return all bottles and unused capsules at the Weeks 4, 8 and 12 visits and will be dispensed a new kit of study drug at the Weeks 4 and 8 visits. In addition, patients in the first cohort of Part 1 will return all unused capsules at the Week 2 visit and will be dispensed a new kit of study drug at that time. Compliance will be measured by counting capsules to determine the number of missed doses from one visit to the next. Patients will also be provided a dosing diary to document that capsules were taken as instructed as well as the date and time of dosing (Section 9.9.20). To be considered compliant with study drug, patients can miss no more than 25% of the total planned doses (i.e., 21 doses) during the study. Patients who exceed the number of allowed missed doses will be considered noncompliant with dosing. Patients will not be discontinued from the study drug nor terminated from the study for noncompliance, but protocol deviations should be recorded for dosing noncompliance.

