#### Figure 1: Schema for Study of RTA 408 in Patients with Mitochondrial Myopathy

T Intra-patient dose escalation by Investigator once each patient reaches Week 2

‡ DSMB review of each cohort once eighth patient reaches specified visit

\*A blinded sample size recalculation may increase the sample size to 12 patients per treatment group in Part 2.

A schema for the protocol is shown in Figure 1 and a detailed schedule of assessments for the study is shown in Table 3. All qualified patients enrolled in the study (i.e., both Part 1 and Part 2) will follow nearly identical schedules of assessments (Table 3) and study drug administration. Patients will self-administer study treatment once daily until they have completed 12 weeks (84 days) of study treatment, are discontinued from study treatment, or have withdrawn consent to participate in the study. A follow-up visit for safety will occur at Week 16 (4 weeks after last dose). The DSMB will perform monthly reviews of unblinded data for safety throughout the study (i.e., during both Part 1 and Part 2).

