#### Table 3:Overall Schedule of Assessments

a These procedures should be performed for early termination.

b Screening procedures for each patient should occur over the course of a few days and must finish at least 1 day prior to randomization. Study Day -1 is the day prior to first dose of study drug.

- c All Day 1 procedures should be performed prior to administration of first dose of study drug.
- d Assessments for Visit 3 may be collected at a home health nurse visit (at appropriate locations and approved by Sponsor) or at the study center clinic.
- e Assessments for Visit 4 must be collected at the study center if patients are enrolled in Part 1 of the study. If patients are enrolled in Part 2 of the study, Visit 4 assessments may be collected by a home health nurse.
- f Visit 6 should be conducted within 18 hours to 48 hours of Visit 5, and Visit 11 should be conducted within 18 hours to 48 hours of Visit 10.
- g For patients with echocardiograms and electrocardiograms collected within 30 days prior to the Screening Visit, the most recent echocardiogram and electrocardiogram can be used to assess cardiac function and patient eligibility.
- h At Week 2, electrocardiogram is only required for patients in Part 1 of the study.
- i A home health nurse visit may be used to collect all lab samples required at the Screening Visit.
- j Patients must be allowed to rest for a minimum period of 1 hour following maximal or submaximal exercise testing before this blood sample is collected (at the same time as all of the central lab blood collection). This sample must be taken prior to the 6MWT. This sample should be taken with the patient in the same position (e.g., sitting or semi-recumbent) at all appropriate visits
- k Blood samples will be collected to analyze for hepatitis B and C and HIV antibodies only in patients lacking evidence of a negative titer in the past year.
- Negative serum pregnancy test results are required at the Screening Visit before study enrollment, and negative urine pregnancy test results are required at all other times indicated for continued participation in the study.
- m At Week 2, study drug dispensation is only required for patients in the first cohort of Part 1 of the study.
- n A dosing diary check must be performed at study drug return and pill count.

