- o At Week 2, study drug return, pill count, and diary check are only required for patients in the first cohort of Part 1 of the study.
- p Study drug should be administered in the presence of study staff in the clinic on Day 1 after all Day 1 assessments have been completed. Study drug should also be administered in the clinic on Days 14, 28 (Part 2 only), 56 (Cohort 1; Part 1 only) and 84 after the blood collection for predose PK analysis. All other doses can be administered at home. RTA 408 should be administered once daily through Day 84.
- q On study days where multiple assessments are to be completed, the maximal exercise test will be the first functional assessment performed. Blood samples will be collected at rest, at the completion of the test, and at 5 and 10 minutes after the test. Maximal exercise testing should be repeated prior to randomization if the original Screening assessment was performed >30 days prior to Day 1.
- r As part of the submaximal exercise test, blood samples will be collected at rest and at 10-minute intervals throughout the test.
- s Muscle needle biopsy, which is optional, should be collected after all study visit assessments are performed, except on Day 1, in which muscle needle biopsy should be the second to last procedure performed, collected prior to study drug administration.
- t For patients enrolled in the first cohort of Part 1 of the study, blood samples for PK analysis at Visit 4 and Visit 8 should be collected prior to study drug administration as well as 1, 2, 4, and 8 hours after study drug administration. A single blood sample for PK analysis at Visit 11 should be collected prior to study drug administration.
- u For patients enrolled in the second and subsequent cohorts of Part 1 of the study, blood samples for PK analysis at Visit 4 should be collected prior to study drug administration as well as 1, 2, 4, and 8 hours after study drug administration. A single blood sample for PK analysis at Visit 11 should be collected prior to study drug administration.
- v For patients enrolled in Part 2 of the study, blood samples for PK analysis at Visit 6 and Visit 11 should be collected prior to study drug administration.
- w Blood collection for biomarkers will be optional. On Day 1, blood collection for blood biomarkers must occur prior to study drug administration.

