#### 9.9.19. Study Drug Dispensation

Enough study drug will be dispensed to the patient at the times indicated in Table 3 to last at least until the next study visit, along with instructions for use.

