### 9.9.21. Study Drug Administration

As outlined in Section 9.1, study drug treatment kits will contain either three or four 30-count bottles of RTA 408 or placebo capsules. Patients should take 1 capsule from each bottle daily. Patients should self-administer study drug orally once daily in the morning on an empty stomach (approximately 1 hour before or 2 hours after eating). Study drug should be taken with water at the times indicated in Table 3, except on Days 1, 14, 28 (Part 2 only), 56 (Cohort 1; Part 1 only), and 84 when study staff will administer study drug at the clinic following all assessments on Day 1, and after the pre-dose blood sample for PK on Days 14, 28 (Part 2 only), 56 (Cohort 1; Part 1 only), and 84. The date and time of the most recent 2 doses of study medication prior to Days 14, 28 (Part 2 only), 56 (Cohort 1; Part 1 only), and 84 will be recorded for PK analysis. The date and time of the last study drug administration (Day 84) should be recorded.

A vomited dose should not be replaced. Missed doses may be taken in the afternoon or evening of the same day approximately 1 hour before or 2 hours after a meal. A double dose (e.g., missed dose from previous day and dose for current day) should not be taken.

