# 10.2. Study Drug Packaging and Labeling

RTA 408 active and placebo capsules are contained in identical primary container closure systems (i.e., 75-cc high-density polyethylene [HDPE] bottles with a foil induction-seal liner and a child-resistant closure). Treatment kits containing either three or four bottles, depending on treatment assignment will be provided to patients for self-administration. Each bottle will contain 30 capsules and a desiccant insert that must not be ingested. The label on each bottle will include the following information:

- Protocol 408-C-1403
- Medication ID number
- Caution statement: New Drug Limited by Federal Law to Investigational Use (United States [US]); For Clinical Trial Use Only (Non-US countries)
- Storage: Controlled room temperature, 20°C to 25°C (68°F to 77°F in the US), with excursions allowed between 15°C and 30°C (59°F to 86°F in the US)
- Sponsor name, address, and contact information
- Contents: One bottle containing 30 capsules of either RTA 408 or placebo. Bottle also contains one desiccant insert, which should not be ingested
- Directions for use: Take capsule as directed, orally, once daily in the morning on an empty stomach (1 hour before or 2 hours after eating) with water
- Keep out of sight and reach of children

- FOR ORAL USE ONLY
- Lot number (Non-US countries)
- Expiration date (Non-US countries)
- Study contact (Non-US countries)
- EudraCT number: 2014-003501-15 (European Union countries)

Additionally, expiry information will be provided on treatment kits intended for use in the EU.

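### One 30-dose kit cannot cover the longest intervals that the visit windows permit, including the one to the primary test, and the schedules leave open what Day 84 means

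*Protocol*

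**What the plan says.** Protocol section 9.3 has all patients "return all bottles and unused capsules at the Weeks 4, 8 and 12 visits and will be dispensed a new kit of study drug" at Weeks 4 and 8, so nothing carries over from one kit to the next. Section 9.1 describes kits of three or four bottles, "each containing 30 count of either active or placebo capsules", section 10.2 repeats the bottle size ("Each bottle will contain 30 capsules and a desiccant insert that must not be ingested"), and section 9.9.21 adds: "Patients should take 1 capsule from each bottle daily".

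Section 9.9.19 requires enough drug at each dispensing visit "to last at least until the next study visit". Section 10.4 says the same and adds that dosing is to be continuous.

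The windows are in Tables 3, 9 and 10: Visit 5 on Day 27 ± 3, Visit 8 on Day 56 ± 3, Visit 10 on Day 83 ± 3. Visit 6 follows Visit 5 by 18 to 48 hours, and "Visit 11 should be conducted within 18 hours to 48 hours of Visit 10". The Week 12 maximal exercise test, which gives the primary endpoint, is at Visit 10. The walk test, the submaximal test and the predose PK sample are at Visit 11.

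On the end of treatment, section 7.1 has patients take drug "until they have completed 12 weeks (84 days) of study treatment", and the dosing footnote of Table 3 says "RTA 408 should be administered once daily through Day 84". Tables 9 and 10 and SAP Table 1 repeat that rule. The same footnotes and section 9.9.21 have the Day 84 dose given by staff after the predose PK sample.

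**The concern.** Two sets of rules do not fit together. The kit holds 30 doses, while the windows allow intervals between dispensing visits, and from the last dispensing visit to the Week 12 tests, that are longer than 30 days. With all leftovers handed back and one new kit given, a patient who keeps every appointment in window can run out of drug before the next clinic visit. Dosing is also said to end on Day 84, although Visit 10 may fall as late as Day 86 and Visit 11 as late as Day 88.

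At stake is whether a patient who follows the protocol is still taking drug on the day peak work is measured, and whether the Visit 11 predose PK sample follows an unbroken run of doses. SAP section 6.1, which covers Part 1, uses all scheduled peak work values through Week 12 and sets no condition on the time since the last dose, so such gaps would not show in the analysis.

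**Working it through.** **Inputs.** 30 capsules per bottle (9.1, 10.2), one per bottle per day (9.9.21): one kit = 30 dosing days. Windows from Table 3, with 18 to 48 hours taken as 1 or 2 calendar days:
- Visit 5: Days 24 to 30; Visit 6: Days 25 to 32
- Visit 8: Days 53 to 59
- Visit 10: Days 80 to 86; Visit 11: Days 81 to 88

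**The plan's own figures.** Planned doses 12 × 7 = 84; permitted misses 0.25 × 84 = 21. Both agree with section 9.3 and SAP section 5.2.

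**Target days.** Days 1 to 27 need 27 doses, Days 28 to 55 need 28, Days 56 to 84 need 29. One kit covers each.

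**Longest permitted intervals.** The first figure stops the day before the later visit; the second counts both visit days.
- Day 1 to Visit 6 (Day 32): 31 or 32. The number of kits given on Day 1 is not stated, and Cohort 1 of Part 1 receives another kit at Week 2, so this interval carries less weight.
- Visit 6 (Day 25) to Visit 8 (Day 59): 59 − 25 = 34, or 35.
- Visit 8 (Day 53) to Visit 10 (Day 86): 86 − 53 = 33, or 34.
- Visit 8 (Day 53) to Visit 11 (Day 88): 88 − 53 = 35, or 36, if dosing continues to Visit 11.

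**The primary test.** There are 7 × 7 = 49 permitted Visit 8/Visit 10 day pairs.
- Kit started on the day of Visit 8: last dose on day V8 + 29. No capsule is left for the test day when V10 − V8 ≥ 30. With V8 = 53 + a and V10 = 80 + b (a, b from 0 to 6), this means b − a ≥ 3, which gives 4 + 3 + 2 + 1 = 10 pairs.
- Visit 8 dose taken from the old kit: last dose on day V8 + 30, so b − a ≥ 4, which gives 3 + 2 + 1 = 6 pairs.
- At least one full day without drug before the test day: 6 pairs and 3 pairs respectively.
- Worst case: kit started on Day 53, last dose on Day 82, test on Day 86. Days 83, 84 and 85 are without drug, and the test is 4 days after the last dose (3 days if the Visit 8 dose came from the old kit).

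**Day 84 on each reading.**
- Calendar day: a Visit 10 on Day 85 or 86 comes 1 or 2 days after the last dose, and a Visit 11 on Day 88 comes 88 − 84 = 4 days after it. A staff-given Day 84 dose is impossible at a Visit 11 on Days 85 to 88. The last kit must cover at most 84 − 53 + 1 = 32 doses, so it is at most 2 short.
- Label for Visit 11: the contradiction with the staff-given dose disappears, but dosing may run to Day 88 and the last interval needs up to 35 or 36 doses.

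**Missed doses from supply alone**, assuming also a single kit on Day 1. The largest total comes from Visit 6 on Day 32, Visit 8 on Day 53 and Visit 11 on Day 88: (31 − 30) + (35 − 30) = 6 before Visit 11, or 7 counting the Visit 11 dose. The limit is 21.

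**The case against.** The strongest reply is that sections 9.9.19 and 10.4 already settle the matter: a site that follows them would dispense more than one kit when an interval is long. The single kit is an inference from the singular in section 9.3, and SAP section 5.2 works from the total number of kits recorded, without fixing it at one. This stands in part, which is why the point is conditional on one kit. But it leaves 9.3 in conflict with the other two sections. The literal next visit after Week 8 is also the Week 10 telephone contact, so meeting their wording does not secure supply to Week 12. Kits are assigned by the IWRS (9.5), so the quantity should be set centrally.

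The second reply is that Day 84 is the nominal day of Visit 11, as Days 14, 28 and 56 in the same footnote are nominal days of visits with windows. That reading is reasonable, and on it a patient with enough supply is still on drug at Visit 10. A reader might infer that dosing has certainly ended before a late Visit 10; the documents do not establish that. Nor do they exclude it, given the 84-day treatment period.

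A reader might also apply the 35 to 36 doses and Day 88 to the primary endpoint. They belong to Visit 11; the figures for the primary test are 33 to 34 doses and Day 86. Nor can 36 doses and a calendar Day 84 stop hold for the same patient, since the first assumes dosing to Day 88.

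**Conclusion.** The conflict is real and should be corrected. If section 9.3 means one kit, it cannot meet 9.9.19 and 10.4 across the permitted windows, and it leaves no capsule for the day of the primary test in 10 of 49 permitted Visit 8/Visit 10 day pairs, or 6 of 49, with at most 3 full days off drug before that test. Day 84 is ambiguous, and each reading clashes with another rule: a calendar day with the late part of the windows and the staff-given dose, a visit label with the 30-dose kit.

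This rests on one kit per dispensing visit, no carry-over, daily dosing without other missed doses, and visits inside their windows. It does not arise when visits are on target.

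Three stronger conclusions are tempting and not supported. The pair counts are not the share of patients who would be affected, because the documents say nothing on how visits spread within their windows. The gap cannot be said to dilute the treatment contrast: nothing in the documents shows how 1 to 4 days since the last dose affects peak work. And these misses alone would not make a patient noncompliant, since 6 or 7 is well below 21.

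**What to change.** Reconcile sections 9.3, 9.9.19, 9.9.21 and 10.4, the dosing footnotes of Tables 3, 9 and 10, and SAP Table 1 with the visit windows.

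1. State in section 9.3, and set in the IWRS, a dispensed quantity that covers the longest permitted interval to the next dispensing or end-of-treatment clinic visit, consistent with whatever end of dosing the sponsor confirms. Say which visit sections 9.9.19 and 10.4 refer to after Week 8.
2. The sponsor should state, identically in every schedule, whether Day 84 is a calendar day or Visit 11. No dosing rule is proposed here.
3. Derive days since last dose at Visits 10 and 11 from the diary dates and times already collected under section 9.9.20, so that any gap is visible beside the Week 12 results.

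The cost is a protocol clarification, an IWRS setting and some extra capsules. No visits, patients or assessments are added.
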